On the other hand, theories have suggested that the drawbacks encountered with the sliding mechanics for incisors retraction can be overcome by the use of well-designed loops providing a better control over the moment/ force ratio and thus the position of anterior teeth. However, minor errors in the loops design can result in major differences in tooth movement, and some patients may find the loops uncomfortable[9].

It is well known that the amount of tip, torque, extrusion/intrusion in anterior teeth is very critical as it affects the final aesthetic outcome. Accordingly,

anterior segment vertical and horizontal control is considered a primary concern to all orthodontists. Despite the large number of studies dealing with mechanics of space closure, little evidence has been found in the orthodontic literature regarding the best guidelines for anterior teeth position after anterior teeth retraction. Therefore, a recent systematic review has recommended additional studies to determine the best way for anterior segment retraction.[11]

There's scarcity in literature concerning the issue of anterior segment retraction technique and its effect on anterior teeth position. Therefore, a randomized clinical trial has been chosen to investigate this issue, aiming to support clinicians with the best guidelines for anterior segment retraction.

Review of Literature

It's widely accepted that one of the main goals seeking orthodontic treatment is aesthetic[12]. Aesthetics are mainly determined by controlling the position of the anterior teeth. Accordingly, three-dimensional control of anterior teeth during orthodontic treatment is important to avoid any side effects on the dentition which might happen due to the applied orthodontic mechanics. Several approaches have been implemented to control both the anteroposterior and the vertical positions of the incisors with multiple studies conducted to evaluate their effectiveness.

- The review of literature will be discussed under the following titles:
 1. Friction mechanics for anterior segment retraction.
 2. Frictionless mechanics for anterior segment retraction.
 3. Friction vs. frictionless.
 4. CBCT for evaluation and its reliability.

1) Friction mechanics for anterior segment retraction

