4. After patient's enrolment, each participant will be asked for pre-intervention records to ensure proper diagnosis.
5. The co-supervisor will randomly allocate the patients to one of the intervention groups.
6. Active intervention will start after proper leveling and alignment of the upper and lower arches and canine retraction.
7. The principle investigator will take pre-retraction records for every participant (T0).
8. In Friction mechanics group, Power chain will be used for anterior segment retraction while in Frictionless group, T-loop will be used for retraction.
9. Each patient will come every 4 weeks for the follow up visit, for appliance activation and impressions for interim records.
10. After complete space closure, the principle investigator will take post-retraction records for each participant (Tfinal).
11. The principle investigator will continue the normal treatment and achieve proper finishing for every patient after the end of the study.

E] Sample size calculation:

In a previous study by **Dincer et al.** [1], they compared the effect of frictionless mechanics via PG spring (Poul Gjessing spring) (Group I) and friction mechanics using coil spring (Group II). The mean change in distance between central incisor edge and x-axis was of 0.68mm and SD of 0.73 in Group I, while Group II was -0.32mm and SD of 0.79.

Sample size calculation was done based on that study using PS software output. A continuous response variable from independent Group I and Group II subjects was planned. In the previous study, the response within each subject group was normally distributed with standard deviation 0.76. If the true difference in the Group II and Group I means is 1.0, we needed to study 10 Group II subjects and 10 Group I subjects to be able to reject the null hypothesis. The population means of the Group II and Group I are equal with probability (power) 0.8. The Type I error probability associated with this test of this null hypothesis is 0.05. Considering drop out a sample size of 15 per group was planned (**Figure 1**).

[figure not shown]

Figure 1: Power curve for 2-sample t-test denoting the power of the study.

Statistical Methods

All statistical calculations will be done using computer program IBM SPSS (Statistical Package for the Social Science; IBM Corp, Armonk, NY, USA) release 22 for Microsoft Windows.

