Numerical data will be tested for the normal assumption using Kolmogorov Smirnov and Shapiro Wilk tests. If normal distribution was found; therefore, data will be statistically described in terms of mean \pm standard deviation (\pm SD). Student t test will be used to compare between the study groups for independent samples in comparing normally distributed data. Paired t test will be used within group comparisons in comparing normally distributed data and Two-sided p values less than 0.05 will be considered statistically significant.

F] Recruitment strategy:

The principal investigator will recruit the patients from the clinic of Orthodontic department, Faculty of Oral and Dental Medicine- Future University.

Screening of patients will continue until the total number of participants for the study is collected.

II) Assignment of interventions:

A] Sequence generation:

The supervisor of the study will apply Computer generated random numbers to randomly assign patients to Group A (Friction) or B (Frictionless) using Microsoft Office Excel 2007 sheet. and will write the patient numbers in the first column, and will select function RAND()to generate the randomization number in the second column. These numbers will be sorted according to the randomization number so the first column numbers will be randomly distributed.

B] Allocation concealment mechanism:

The supervisor of the study will write the randomization numbers of the patients in opaque white papers folded three times to form sealed envelopes and store it inside a box. Then will keep the Codes for randomization at the secretary office.

C] Implementation:

At time of intervention, the main operator will send the patient to the secretary office. Then, the assigned employee will open the box and ask the patient to select one envelope. the main operator will assign each participant for the corresponding intervention either (friction or frictionless group) according to the list of codes of randomization.

Assignment to either intervention will occur before leveling and alignment stage.

D] Blinding:

Blinding of the operators: Blinding will not be possible for the operators during the application interventions and during the follow up visits. The principal operator is responsible for assigning subjects to interventions according to the concealed allocation, appliance activation at follow up visits.

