Blinding of the outcome assessors: It is a single blinded study, the outcome assessors only will be blind. The patients name will be sealed from pre and post records. Then two assessors will carry on, blindly and independently, the measurements and analysis of the study.

III) Data collection, management and analysis:

A] Data collection methods:

Primary outcome:

1. *Anterior teeth torque, extrusion/intrusion:* will be assessed by the principle investigator via CBCT taken before and after the completion of retraction. The principal investigator identified the landmarks, reference lines and planes, then interpreted the measurements in degrees and millimeters.

2. *Anterior teeth tip:* will be assessed by the principle investigator via CBCT taken before and after the completion of retraction.

Secondary outcomes:

1. *Root resorption:* will be assessed by the principle investigator via CBCT taken before and after the completion of retraction. The resorption will be identified using scoring system of Levander and Malmgren[21] that classifies it into 5 grades: 0: no root resorption; 1: mild resorption, with the root of normal length and only an irregular contour; 2: moderate resorption, with small areas of root loss and the apex having an almost straight contour; 3: severe resorption, with loss of almost one third of root length; and 4: extreme resorption, with loss of more than one third of the root length.

B] Data management:

A colleague outside the research team will enter the data and organize it in excel sheets in the computer of the orthodontic department.

Data will include all photographs, models and radiographs.

C] Statistical Analysis:

- The principle investigator will be responsible for the extraction of the required data from the CBCT taken before and after retraction. The data will be sent to a specialized statistician.

- The specialized statistician will be responsible for the statistical analysis of the study by:

1. Presenting the data as mean, standard deviation (SD) and Standard error (SE) values.

2. Using Paired t-test to compare between the friction and the frictionless group of retraction as well as to compare between the pre-and post -treatment data for each group.

3. Using Anova test to determine the rate of anterior segment retraction.

4. Statistically evaluate the patient acceptance for both techniques.

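### Name Welch's t test for the between-arm comparison: the plan uses Student's t with no provision for unequal variances, although dropout could leave the arms unequal in size

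*Combined protocol and SAP*

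**What the plan says.** The Statistical Methods section sets the between-arm test: "Student t test will be used to compare between the study groups for independent samples in comparing normally distributed data". It adds that "Two-sided p values less than 0.05 will be considered statistically significant". Normality is to be tested. Equality of variances is not mentioned, and no unequal-variance alternative is named.

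The Statistical Analysis section (Data collection, management and analysis, item 2) gives a different test for the same comparison: "Using Paired t-test to compare between the friction and the frictionless group of retraction".

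The sample size section uses one common SD for both arms ("the response within each subject group was normally distributed with standard deviation 0.76"), a Type I error of 0.05 and power of 0.8. It arrives at 10 per arm and then states: "Considering drop out a sample size of 15 per group was planned". No arm-specific dropout rate is given. Allocation is 1:1.

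The text on variability points both ways. On loops, the introduction says that "minor errors in the loops design can result in major differences in tooth movement, and some patients may find the loops uncomfortable". A little earlier it credits sliding mechanics with weak force control and poor vertical and horizontal hold on the anterior teeth. The only SDs in the documents are for the change in incisor-edge distance in the source study: 0.73 mm frictionless and 0.79 mm friction. No SD is given for torque or tip, which are also primary outcomes.

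**The concern.** Student's t pools one variance across the two arms. If the arms differ in both size and variance, the pooled standard error is biased. It is too small when the smaller arm is the more variable, so the test rejects too often. It is too large when the smaller arm is the less variable, so the test rejects too rarely. The planned 5% error rate would then not hold exactly for the primary comparisons.

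The allowance of 15 for 10 tolerates a loss of one third in each arm, and nothing ensures that losses will be balanced. SPSS also prints both the equal-variance and the unequal-variance result. A plan that provides only for the first leaves room to switch after the results are seen.

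**Working it through.** **1. The plan's own figure.** Inputs from the sample size section: difference 1.0 mm, SD 0.76 mm, two-sided alpha 0.05, power 0.80.

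- Normal approximation: n per arm = 2 × (0.76/1.0)² × (1.960 + 0.842)² = 9.07, rounded up to 10.
- Noncentral t at 10 per arm: noncentrality 1.0 / (0.76 × √(2/10)) = 2.94 on 18 df, power 79.5%.
- Dropout: 10 / (1 − 1/3) = 15, so the implied allowance is 33% in each arm.

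The planned 10, and 15 after dropout, are reproduced.

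**2. Why size and variance matter together.** The squared standard error that Student's t estimates is, on average,

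[(n1 − 1)σ1² + (n2 − 1)σ2²] / (n1 + n2 − 2) × (1/n1 + 1/n2),

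whereas the true value is σ1²/n1 + σ2²/n2. With SDs of 1.5 and 1:

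- 15 v 15: both equal 0.217, so there is no bias.
- Smaller arm more variable (10 with SD 1.5, 15 with SD 1): [(9 × 2.25 + 14)/23] × 0.1667 = 0.248, against 2.25/10 + 1/15 = 0.292. The standard error is about 8% too small.
- Smaller arm less variable (15 with SD 1.5, 10 with SD 1): [(14 × 2.25 + 9)/23] × 0.1667 = 0.293, against 2.25/15 + 1/10 = 0.250. The standard error is about 8% too large.

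**3. Type I error.** For normal data with no true difference, the rejection rate is the average of 2Φ(−c × SE/τ) over the distribution of the two sample variances. Here SE is the test's estimated standard error, τ² = σ1²/n1 + σ2²/n2, and c is the 0.975 quantile of t on n1 + n2 − 2 df (Student) or on Welch's df. This was done by numerical integration, with selected cases confirmed by simulation. Ratios of 1.5 and 2 are assumptions; 0.92 is 0.73/0.79.

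| Analysed, frictionless v friction | SD ratio, frictionless/friction | Student | Welch |
|---|---|---|---|
| 15 v 15 | 0.92 | 5.0% | 4.9% |
| 10 v 10 | 0.92 | 5.0% | 4.9% |
| 10 v 15 | 0.92 | 4.7% | 4.9% |
| 15 v 10 | 0.92 | 5.4% | 5.0% |
| 15 v 15 | 1.5 / 2 | 5.1% / 5.3% | 5.0% / 5.0% |
| 10 v 10 | 1.5 / 2 | 5.2% / 5.5% | 4.9% / 5.0% |
| 12 v 15 | 1.5 / 2 | 6.2% / 7.1% | 5.0% / 5.1% |
| 10 v 15 | 1.5 / 2 | 7.1% / 8.7% | 5.1% / 5.1% |
| 15 v 10 | 1.5 / 2 | 3.6% / 3.0% | 4.9% / 4.9% |

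**4. How far the source SDs settle the ratio.** The literature review gives source groups of 17 and 19. The observed variance ratio is (0.73/0.79)² = 0.854. Dividing by the 0.975 and 0.025 quantiles of F on 16 and 18 df and taking square roots gives a 95% interval of about 0.57 to 1.52 for the SD ratio. At 10 frictionless v 15 friction, Student's error runs from 3.3% to 7.2% across that interval. The interval excludes a ratio of 2 in either direction (1/0.57 is about 1.76), but for this one measure only.

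**5. Cost of Welch when variances are equal.** By simulation (difference 1.0, SD 0.76), power for Student v Welch is 0.796 v 0.791 at 10 per arm, 0.934 v 0.934 at 15 per arm, and 0.868 v 0.860 at 10 v 15.

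**The case against.** The strongest reply is that nothing in the documents predicts a problem. Student's t is robust with equal arms, and allocation is 1:1. The only SDs given are nearly equal, and the frictionless one is the smaller. On those SDs the error is 4.7% to 5.4% whichever arm loses patients. Reaching 7% at a ratio of 1.5 needs a third of one arm lost and nobody from the other, with the larger spread in the depleted arm. All of this stands, and it limits the point to a safeguard.

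A reader might infer more: that the protocol itself expects the frictionless arm to be both noisier and smaller, so that the real error rate is 7% to 9%. The documents do not support that.

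- The remark about loop-design errors is offset by the criticism of sliding mechanics and by the source SDs.
- Discomfort with loops is mentioned, but it is not linked to dropout.
- Assignment comes before leveling and alignment, and loops are placed only after canine retraction. Losses in that long shared phase would not be caused by loops.
- The criteria for discontinuing or modifying treatment concern miniscrews, which both arms use.
- The upper figure of 8.7% needs an SD ratio of 2, which lies outside the source study's interval for the one measure reported.

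The objection does not remove the gap. The source SDs come from a different spring and a single vertical measure, and torque and tip have none. With the direction unknown, Student's t may err either way, and Welch's test protects against both.

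**Conclusion.** The point holds as a minor one. The plan names Student's t, makes no provision for unequal variances, and allows for dropout that could leave the arms unequal. On the documents' own figures, or with equal arms and SD ratios up to 2, the error is about 4.7% to 5.5%, which is no practical problem. It reaches about 7% only when one-sided dropout and a larger SD in the smaller arm coincide: 10 v 15 at a ratio of 1.5, or 12 v 15 at a ratio of 2. At 10 v 15 with a ratio of 1.5 in the opposite direction it drops to about 3.6%. These figures assume normal data, and the ratios of 1.5 and 2 are not from the documents. The case for change is that Welch's test stays near 5% in every pattern checked at almost no cost, not that inflation is expected.

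The between-arm paired t test in the Statistical Analysis section is the larger inconsistency and has to be settled first, since two independent arms provide no pairs. Once an independent-samples test is confirmed, the choice between pooled and unequal-variance forms still has to be written down.

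**What to change.** In Statistical Methods, replace *Student t test* for the between-arm comparison with *Welch (unequal-variance) t test*. State that it is used in all cases and is not chosen by a preliminary test of variances.

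In Statistical Analysis, item 2, remove the paired t test between the friction and frictionless arms so that the two sections agree. Keep the paired test for the before-and-after comparison within each arm.

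The cost is one phrase in each section. SPSS already prints the unequal-variance row. If the variances are in fact equal, the loss of power is under 1 percentage point.

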- For this study, the specialized statistician used IBM11 SPSS12 Statistics Version 20 for Windows to perform the required statistics.

- The significance level will be $P \leq 0.05$. Highly significant variables are detected when P value is less than 0.01.

Assessors Reliability:

- To achieve high reliability for measurements, the supervisor will choose a well-experienced inter-examiner during the study.
- A training session will be provided for the examiners to ensure standard measurements techniques.
- Each examiner will complete the measurements on a model and will repeat the procedure after one week to assess the intra- and inter-examiner reliability.
- The supervisor will compare the measurements of the two assessors for disagreement with a difference of more than one millimeter.
- The supervisor will evaluate the amount of variation in measurements among and between examiners to test the performance of each assessor.
- The examiner with less reliability will receive additional training but will be replaced during the study.
- The specialized statistician will calibrate the intra and inter-examiner reliability for the measurements of the study by Inter-observer and intra-observer reliability will be assessed using $P \leq 0.05$.

IV) Method Monitoring:

A] Data Monitoring: An independent Data Monitoring Committee (DMC) will monitor the results of the study. The Committee will include the trial's supervisors, who will periodically review the trial data and identify the need for any adjustments or modifications during the study.

B] Interim Analysis: no interim analysis will be performed during the study.

C] Harm: The main operator will document and report any harms or unwanted effects during the study intervention to the trial supervisors. Also, any unpleasant experience will be reported by the patient in the final questionnaire at the end of the retraction. The main operator will be responsible for the management of any adverse effects or unfavorable side effects resulting from the appliance.

D] Auditing: The supervisor will follow up and review the different interventions and resulting data. And he will periodically follow up the trial progress including recruitment of patients, allocation of participants to study groups; adherence to interventions and reporting of harms. A meeting with the senior supervisor will be set every 3 months to monitor the progress of the study and the need for any adjustments.

V) Ethics and dissemination:

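### The plan gives two allocation times, and under the explicit early one the unblinded operator knows the arm during the shared preparation and patients lost before T0 are randomised without an outcome

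*Combined protocol and SAP*

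**What the plan says.** **Time of allocation.** Section II, C] Implementation, makes two statements. It opens with "At time of intervention, the main operator will send the patient to the secretary office", where the patient draws an envelope. It closes with "Assignment to either intervention will occur before leveling and alignment stage". In the participant timeline, item 5 reads "The co-supervisor will randomly allocate the patients to one of the intervention groups". Item 6 starts active intervention after levelling, alignment and canine retraction, and item 7 is the T0 record.

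**Shared preparation.** Clinical Procedure describes bonding, the wire sequence, miniscrews, extractions and canine retraction once, for all patients. The arms separate only under Start of Retraction, after the T0 CBCT.

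**Outcomes.** Section D] Outcomes measures every outcome as the difference between T0, after full canine retraction, and T1, after space closure.

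**Who knows the arm.** Under D] Blinding, "The principal operator is responsible for assigning subjects to interventions according to the concealed allocation, appliance activation at follow up visits", and "Blinding will not be possible for the operators during the application interventions and during the follow up visits". Only the outcome assessors are to be blind, so patients are not blinded either.

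**Handling of losses.** The sample size rises from 10 to 15 per group for dropout, with no rate given. Recruitment runs on: "Screening of patients will continue until the total number of participants for the study is collected". Statistical Methods names the group comparison: "Student t test will be used to compare between the study groups for independent samples in comparing normally distributed data". No analysis set or missing-data rule is stated. Auditing is to "periodically follow up the trial progress including recruitment of patients, allocation of participants to study groups; adherence to interventions and reporting of harms"; losses by arm are not named there or elsewhere.

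**The concern.** Randomising before a long stage in which the arms do not differ gains nothing for the comparison and exposes it in two ways.

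- **Loss before T0.** Such a patient counts as randomised but cannot contribute to any outcome. With no analysis set defined, she would simply drop out of the t test.
- **Knowledge of the arm.** The operator who carries out canine retraction and refers the patient for T0 already knows what comes next. The plan gives no measurable criterion for complete canine retraction, so the referral rests on judgement. The patient may know her arm too, and could leave because of it.

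Since treatment before T0 is the same in both arms, a difference between arms in who reaches T0, or when, could arise systematically only through knowledge of the arm. Concealing the arm until T0 closes that route. What is at stake is the comparability of the groups at T0 in a trial that needs only 10 completers per arm.

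**Working it through.** **Step 1. Which allocation time does the plan give?**

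| Place | What it implies |
|---|---|
| Implementation, closing sentence | Before levelling and alignment (explicit) |
| Participant timeline, items 5 to 7 | Allocation, then preparation, then T0 (agrees with early) |
| Implementation, opening sentence, read with timeline item 6 | At the start of active intervention, after canine retraction (late) |

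Two places support early allocation, one of them explicitly. The opening sentence read with item 6 supports late allocation. Early is the better-supported reading, but the section is not consistent.

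**Step 2. What follows from early allocation?** The T0 CBCT comes after canine retraction, and each outcome is T1 minus T0. Without T0 there is no outcome. The operator applies the allocation, so knowledge of the arm spans levelling, miniscrew placement, extraction, canine retraction and referral for T0. Nothing in the text withholds the arm over that period.

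**Step 3. Is the stated sample size affected?** Inputs from Sample size calculation and Statistical Methods: difference 1.0, SD 0.76, two-sided alpha 0.05, power 0.8.

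- Normal approximation: n = 2 × (1.960 + 0.842)² × 0.76² / 1.0² = 9.07, rounded up to 10 per group. The plan's figure reproduces.
- Exact power at 10 v 10: noncentrality = 1.0 / (0.76 × √(1/10 + 1/10)) = 2.942, 18 degrees of freedom, critical t = 2.101, power 0.795.
- The rise to 15 allows for a loss of 1 − 10/15 = 33.3%, before and after T0 together.

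The number of completers required does not depend on when the envelope is opened.

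**Step 4. Does opening the envelope later cost power?** Assumptions, since the documents give no loss rate: 30 enrolled, a box of 15 + 15 envelopes, 20 completers, loss unrelated to arm.

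- *Early opening:* the 20 completers are a random 20 of 15 + 15, so the split is hypergeometric. An 8 v 12 split or worse has probability 0.245; 7 v 13 or worse has probability 0.050.
- *Late opening:* say 25 reach T0 and draw an envelope, and 20 of them complete. A random 20 from a random 25 of 15 + 15 is again a random 20 of 15 + 15. The probabilities are the same, 0.245 and 0.050.

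Power by split, with the same formula:

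| Completers | Power |
|---|---|
| 10 v 10 | 0.795 |
| 9 v 11 | 0.791 |
| 8 v 12 | 0.778 |
| 7 v 13 | 0.756 |

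These losses of power come from having 20 completers out of 30, and apply equally under either timing.

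**Step 5. Can the bias be sized?** No. That would need loss before T0 by arm, or the effect of the operator's knowledge on T0. The documents give neither.

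**The case against.** **The plan may already mean late allocation.** The opening sentence of Implementation, read with timeline item 6, puts the draw near T0. This stands as far as it shows a contradiction. It does not displace the explicit closing sentence, which the timeline order supports.

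**The harm is hypothetical.** Preparation follows one protocol, no passage gives the operator a reason to treat or lose patients differently by arm, and randomising early with later divergence is a legitimate design. This largely stands. A reader might infer that the comparison will be biased; the documents do not support that. A reader might also infer that any shift at T0 biases the result. A shift that persists to T1 cancels in the change score; it matters only if it alters later movement or the space left to close.

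**Safeguards exist.** Auditing covers allocation and adherence, and its list may not be exhaustive. Two blinded assessors are planned, and 15 per group allows for losses. None of this hides the arm before T0. The allowance protects power, not balance between the arms.

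**The missing analysis set is a separate defect.** True: it would exist whatever the allocation time. So would the conflict over the test, since section III, C] Statistical Analysis names a paired t test between the groups. Neither test adjusts for T0, and neither can include a patient without T0.

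**Conclusion.** The point holds as a contradiction to reconcile and, under the explicit early timing, as an avoidable risk of bias. It rests on three readings of the text: that the explicit sentence and the timeline order govern, that preparation is the same in both arms, and that the operator learns the arm at assignment. The size and direction of any bias cannot be derived, and none is shown.

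Two stronger inferences should be resisted. The sample size is not undermined: 10 completers per group is needed under either timing. Nor does late opening carry a cost in power: with the same 30 enrolled and loss unrelated to arm, the split of completers has the same distribution either way. Late opening would leave more completers only if 15 per group were randomised at T0, which would mean enrolling more than 30 whenever anyone is lost beforehand.

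The change is a cheap improvement that should be made.

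**What to change.** State one allocation time.

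- **Implementation.** Replace the closing sentence on timing with: *The envelope is opened after canine retraction is complete and the T0 CBCT has been acquired, immediately before anterior segment retraction starts.* Change the opening phrase to: *After the T0 CBCT.* Keep the concealed draw.
- **Participant timeline.** Move item 5 after item 7. In doing so, reconcile who allocates: item 5 names the co-supervisor, while Implementation has an office employee present the box and the main operator apply the code.
- **Sample size calculation.** Replace the planned 15 per group with: *30 patients are enrolled (10 per group needed, plus dropout allowance); those reaching T0 are randomised 1:1.*
- **Reporting.** Report losses before T0, and losses after T0 by arm.

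**Cost.** Wording and a later opening of the envelope; no extra patients, visits or scans. Fewer than 15 per group may be randomised, and patients who leave before T0 are reported as enrolled but not randomised.

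**If early allocation is kept.** Keep the envelope sealed and the arm withheld from operator and patient until T0 has been acquired, and report losses before T0 by arm. Adjusting the comparison for the T0 value is not a substitute: it neither hides the arm nor recovers patients who have no T0.

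### The plan provides no masking of the statistician, who must choose between two conflicting between-group tests; fix the test first, then send coded arms

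*Combined protocol and SAP*

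**What the plan says.** **Who is blind.** Section II) D] Blinding rules out blinding the operators and then states: "It is a single blinded study, the outcome assessors only will be blind". It continues: "Then two assessors will carry on, blindly and independently, the measurements and analysis of the study".

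**Who analyses.** Section III) C] Statistical Analysis says "The data will be sent to a specialized statistician" and "The specialized statistician will be responsible for the statistical analysis of the study by" a list of steps. It does not say whether the file carries arm names, group letters or only patient numbers.

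**Which test.** The Statistical Methods section, after the sample size calculation, says "Student t test will be used to compare between the study groups for independent samples in comparing normally distributed data". Section III) C] says "Using Paired t-test to compare between the friction and the frictionless group of retraction". Neither section says how measurements on several anterior teeth become one value per patient.

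**Codes and data handling.** Section II) A] Sequence generation openly defines Group A as friction and Group B as frictionless. Section V) D] Confidentiality uses coded patient numbers to protect identity. Section III) B] Data management says "A colleague outside the research team will enter the data and organize it in excel sheets", and counts photographs, models and radiographs as data. Section V) F] restricts data access to the supervisors and the principal investigator.

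**The concern.** Masking the analyst matters most when decisions remain open after the data are in, and here several do. The two statistics sections give incompatible between-group tests, and the reduction from teeth to patients is unspecified. If the statistician knows the arms, each choice can be made, knowingly or not, with sight of which arm it favours. The trial is small, is funded by the principal investigator, and has that same role extracting the CBCT data, so it gains from any safeguard that costs almost nothing. What is at stake is a directional lean in the result, which an overall error rate would not reveal.

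**Working it through.** **1. The plan's own figure.** Inputs from the sample size section: difference 1.0 mm, SD 0.76 mm, type I error 0.05 (two-sided, per Statistical Methods), power 0.80.

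n per group = 2 × (1.960 + 0.842)² × SD² / difference² = 2 × 7.849 × 0.5776 / 1.0 = 9.07, rounded up to 10.

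The stated 10 per group reproduces. The exact noncentral-t solution is 10.12, with power 0.795 at 10. This is a calculation for independent groups, so the paired test does not match the basis on which the trial was sized.

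**2. How often the two documented tests disagree.** 200,000 null trials were simulated at each size, with normal data, equal variances and pairing by arbitrary order (a parallel-group design offers no real pairs). Both tests were applied two-sided at 5%.

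| Per arm | Independent t | Paired t | Tests disagree | Smaller P < 0.05 |
|---|---|---|---|---|
| 10 | 5.0% | 4.9% | 2.9% | 6.4% |
| 15 | 5.1% | 5.0% | 2.5% | 6.3% |

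The smaller-P rate follows from the disagreement rate. Each test rejects about 5% of the time, so the smaller P rejects in about 5% + d/2 of trials and the larger P in about 5% − d/2. At 15 per arm, d = 2.5% gives about 6.25% and 3.75%.

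**3. What the labels add.** Both two-sided P values are unchanged when the arms are swapped (checked in the simulation). Taking the smaller P therefore works equally well on masked data, and the rise to about 6.3% is not an effect of unmasking.

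An analyst who knows the arms can do something different: take the smaller P when the favoured arm leads and the larger P when it does not. By symmetry, each direction gets half of the corresponding rate. At 15 per arm:

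- towards the favoured arm: 6.25% / 2 ≈ 3.1%
- against it: 3.75% / 2 ≈ 1.9%
- total: 3.1% + 1.9% = 5.0%

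The simulation gave 3.1% and 1.9% at 15 per arm, and 3.2% and 1.7% at 10 per arm, against 2.5% and 2.5% for a single fixed test.

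**4. Stability.** A repeat with 1,000,000 trials per size gave smaller-P rates of 6.5% (10 per arm) and 6.2% (15 per arm), and splits of 3.2%/1.8% and 3.1%/1.9%.

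**5. Each remedy.** Fixing one test returns the error to 5%, split evenly, as far as test choice is concerned. Masking alone removes the tilt but leaves the smaller-P inflation in place. Neither changes sample size or power.

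**The case against.** **The statistician may in fact be masked.** The sentence on blinding sits under the assessor heading and may only contrast assessors with operators and patients. The same paragraph has two assessors carry out blinded analysis as well as measurement, and the format of the file sent to the statistician is not described. This stands in part. A reader might infer that the statistician certainly sees which arm is which; the documents do not establish that. They do establish that no masking is provided. The blind analysis in that paragraph belongs to the assessors, while the statistical analysis goes to another role. The coded numbers serve confidentiality, and A and B are decoded in the protocol itself.

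**The larger inflation is not caused by unmasking.** This stands in full. A reader might attribute a type I error of 6% or more to the unmasked analyst, or add a rank test to the options and obtain a higher figure. Smallest-P selection needs no labels, and the plan names no non-parametric test.

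**The root cause is the unfixed analysis.** This also stands. Once one test and one patient-level summary are fixed, masking is a secondary safeguard. It still protects choices that remain, such as the handling of outliers.

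**Masking is not free.** The data-access text limits access to the supervisors and the principal investigator, so giving the key to an outside colleague requires an edit. The cost is small but not nil.

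**Conclusion.** The point holds as a modest, cheaply corrected weakness. The plan limits blinding to the outcome assessors and leaves an unmasked role to choose between conflicting tests. Knowledge of the arms could shift the false-positive split from 2.5%/2.5% to about 3.1%/1.9% at 15 per arm, with the total still near 5%.

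These figures assume normal data, equal variances, arbitrary pairing, a choice between the two documented tests only, and an analyst who always exploits the choice. Choices of teeth, arch or outliers are not included. The figures show what is possible and do not predict conduct.

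It would be wrong to conclude that masking by itself repairs the analysis. It would also be wrong to take assessor blinding as settled. Section III) A] has the principal investigator assess every outcome, and the Participant timeline has the same role take the T0 and final records and continue each patient's treatment. That contradiction is a separate and more serious blinding problem.

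**What to change.** 1. Name one between-group test in advance in both statistics sections: the independent-samples test, which matches the parallel design and the sample-size basis. State the rule that reduces teeth to one value per patient. Keep the paired test for within-group change only.
2. Have the outside data-entry colleague send the statistician numerical data only, since photographs could reveal the appliance. Arms should be labelled X and Y, not the already decoded A and B. The colleague holds the key and releases it once the analyses and results tables are locked.
3. Amend section II) D] to say that the statistician is masked, and reconcile section V) F] with the access that the colleague and the statistician need.
4. Before restating that assessors are blind, reconcile the two blinded assessors in II) D] with the principal investigator's role in III) A].

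The cost is a recoded column and a short amendment through the process in V) B]. Sample size, power and treatment are unaffected.
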